Figure 3. In order to optimize rTMS for neurcognitive enhancement, it is essential to determine the dose-response curve.

accelerated rTMS will promote stress resilience and prevent the onset of neuropsychiatric symptoms (e.g., anxiety, depression, anger, irritability).

Study Arm 1 would establish the dose-response for enhancing cognitive performance with accelerated rTMS to left dIPFC. Stress resilience will be utilized as a secondary outcome. Given the model it would also be reasonable to first establish the objective point at which resilience is up regulated by rTMS. We anticipate that healthy participants analogous to astronauts would likely show little variability in baseline resilience and affective dysfunction. We also anticipate that rTMS as proposed here could prevent the onset of stress and neuropsychiatric symptoms and thus we will longitudinally follow participants for the emergence.

Study Arm 2 would utilize the dose established in study one that maximizes cognitive performance gains while minimizing side effects and burden in a double blind, randomized controlled trial. Primary (neurocognitive performance) and secondary (resilience) outcomes would be identical to study 1. In addition, the impact of active versus sham iTBS on cognitive control and resilience under stress will be demonstrated during a challenging learning paradigm under threat of shock. EEG will be used to assess the impact on of iTBS on neurocircuit structure and function. Response stability will be assessed at 6 months and one year. To assess safety, structural MRI adverse event reporting, and cognitive measures will be collected over a long-term 6-month follow up period.

Study Arm 3 study would assess the biological efficacy of TMS in a microgravity environment during parabolic flight.

Study Arm 4 would establish the dose-response for enhancing cognitive performance with accelerated rTMS to left dIPFC, as well as assessing safety. In addition, the impact of each dose of iTBS on cognitive control and resilience under stress will be demonstrated during a challenging learning paradigm under threat of shock. MRI and EEG will be used to assess the impact on of iTBS on neurocircuit structure and function. Response stability will be assessed at 1 month post-treatment. Approval to combine studies 1 and 2 into a 4th arm was approved by our sponsor, due to recruitment delays caused by COVID-19.

B. INNOVATION AND ADVANTAGES AND RELEVANCE TO ASTRONAUTS

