7	Neurocognitive Battery Questionnaire Battery	MUSC Brain Stimulation Laboratory in the Institute of Psychiatry	90 minutes 1 hour
8	1 month post-treatment Neurocognitive Battery	MUSC Brain Stimulation Laboratory in the Institute of Psychiatry	90 minutes 1 hour

1 month post-treatment Questionnaire Battery		
---	--	--

*Option to complete remotely due to COVID-19 precautions.

Study Arm 2: Efficacy & Safety

Assessment & rTMS. The assessment and TMS methods from study 1 will be identical, except that 60 participants (enrollment n=70 to complete assessments and treatment for n=60 to contend with drop out) will be randomized to one dose of active or sham iTBS rTMS. **The dose will be determined as the most efficacious dose from Study 1, minimizing side effects and burden.** In addition, to determine longer-term safety of the intervention, participants will complete neurocognitive, resilience and symptom measures pre- and immediately post-treatment as well as 1, 2, and 6 months later.

MRI assessment. To more specifically examine safety, participants who received active stimulation will undergo MRI sessions (FLAIR, diffusion, T2* and volumetric sequences) for assessment of structural changes at pre- and post-treatment, and 6 months later.

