Table 3. Visit Summary Study Arms 2 and 4: Dose-finding/Efficacy & Safety

Session Number	Task Description	Location at MUSC	Visit Duration
0	Eligibility Screening	Telephone	30 minutes
1	Consent	MUSC Brain Stimulation Laboratory in the Institute of Psychiatry	20 – 30 minutes
	Interview		30 minutes
	Neurocognitive Battery		90 minutes
	Questionnaire Battery		1 hour
	Motor Threshold Testing		10 – 15 minutes
2	MRI Safety Screen	MUSC Center for Biomedical Imaging	5 minutes
	Pre-treatment Structural MRI and functional MRI		1 – 2 hours
	EEG assessment		1-2 hours
3	rTMS	MUSC Brain Stimulation Laboratory in the Institute of Psychiatry	Up to ten 3-minute treatment sessions separated with 20-30 minutes or more between each session. Total Time: 3 - 5 hours
4	rTMS	MUSC Brain Stimulation Laboratory in the Institute of Psychiatry	Up to ten 3-minute treatment sessions separated with 20-30 minutes or more between each session. Total Time: 3 - 5 hours
5	rTMS	MUSC Brain Stimulation Laboratory in the Institute of Psychiatry	Up to ten 3-minute treatment sessions separated with 20-30 minutes or more between each session.

			Total Time: 3 - 5 hours
6	rTMS	MUSC Brain Stimulation Laboratory in the Institute of Psychiatry	Up to ten 3-minute treatment sessions separated with 20-30 minutes or more between each session. Total Time: 3 - 5 hours
7	rTMS	MUSC Brain Stimulation Laboratory in the Institute of Psychiatry	Up to ten 3-minute treatment sessions separated with 20-30 minutes or more between each session. Total Time: 3 - 5 hours
8	Post-treatment Neurocognitive Battery Post-treatment Questionnaire Battery	MUSC Brain Stimulation Laboratory in the Institute of Psychiatry	90 minutes 1 hour
9	MRI Safety Screen Post-treatment Structural MRI and functional MRI EEG assessment	MUSC Center for Biomedical Imaging	5 minutes 1 – 2 hours 1 – 2 hours
10	1 month post-treatment Neurocognitive Battery 1 months post-treatment Questionnaire Battery EEG assessment	MUSC Brain Stimulation Laboratory in the Institute of Psychiatry	90 minutes 1 hour 1 – 2 hours

Study Arm 3: Biological Efficacy of TMS in Microgravity

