The rationale for participant/dose ratio. Dose-response studies are not powered in the traditional manner. In order to resolve the shape of the continuous dose response function, it is statistically more efficient to select more doses as opposed to more participants^{57,58}. The number of observations within each dose is primarily to account for sampling variability, which could be achieved with a minimum of 2 to 3 observations. Capturing variability is essential to the planned analyses, which underweight the points of greatest variability in estimating the response curve. To contend with dropout we propose to enroll 60, with the aim of completing assessments and treatment for 50 participants. We conservatively expect an 80-90% retention rate, as dropout is typically fewer than 10% in double-blind trials of conventional daily⁵⁹ as well as accelerated rTMS³¹.

Arm 2. Descriptive statistics would be performed on acceptability ratings, adverse events, and dropout rates. Linear mixed-effects models would assess group x pre/post rTMS change in neurocognitive performance, resilience and stress self-report measures, and EEG and ERP metrics. Regarding statistical power, we based predicted effect sizes on findings of neurocognitive enhancement by Holtzheimer et al.³¹ in an accelerated rTMS protocol, specifically, reliable change of 5 standard units on the RBANS (SD=8.9). Specifically, group sample sizes of 27 achieve 80% power to detect a difference of 5.000 (SD=8.9) in a design with 3 repeated measurements having a Compound Symmetry covariance structure, the correlation between observations on the same subject is 0.300, and alpha level is 0.050. We propose to enroll 70 people to contend with dropout with target completion reached with 30 participants each completing active and sham conditions (60 participants total).

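### Arm 2's 80% power fits a comparison of three-measurement group means; the planned group x pre/post test has 44–63% at 30 per group (57–77% if 8.9 is a change SD)

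*Combined protocol and SAP*

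**What the plan says.** All of this is in section 10.0, Statistical Plan, Arm 2, unless stated otherwise.

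- **Analysis:** "Linear mixed-effects models would assess group x pre/post rTMS change in neurocognitive performance". No baseline covariate or baseline constraint is mentioned.
- **Effect input:** a "reliable change of 5 standard units on the RBANS (SD=8.9"), taken from a cited study of accelerated rTMS. Section 13.0 describes that result as a change from baseline to six weeks in patients with major depression.
- **Power:** "group sample sizes of 27 achieve 80% power to detect a difference of 5.000 (SD=8.9) in a design with 3 repeated measurements", under compound symmetry, where "the correlation between observations on the same subject is 0.300", at alpha 0.05. Sidedness is not given.
- **Target:** "target completion reached with 30 participants each completing active and sham conditions", that is, 60 completers.

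The follow-up schedule appears in three forms:

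- Section 9.0, Study Arm 2: "participants will complete neurocognitive, resilience and symptom measures pre- and immediately post-treatment as well as 1, 2, and 6 months later", which is four post-treatment visits.
- Table 3 (Arms 2 and 4): neurocognitive testing at baseline, after treatment and at the "1 month post-treatment Neurocognitive Battery", which is two post-treatment visits.
- Section 2.0: "Response stability will be assessed at 6 months and one year".

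**The concern.** The analysis sentence describes a difference between groups in change from baseline. The power sentence describes a difference between groups across three repeated measurements and never says that a baseline is subtracted. These contrasts have different variances. At a within-person correlation of 0.3, below 0.5, subtracting a baseline adds variance instead of removing it, so a sample size derived for averaged levels is too small for an unadjusted change.

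Neurocognitive performance is the primary outcome of Arm 2. If the arm runs as written, the chance of missing a true 5-point effect is 37–56% (23–43% if 8.9 is a change SD), where the plan implies 20%. A null result would then be weaker evidence of no benefit than a reader of the protocol would suppose.

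The effect input is a separate weakness. A before–after RBANS change in depressed patients is used as an active–sham difference in healthy adults, and the RBANS is not in the test battery listed in section 9.0.

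**Working it through.** **Inputs (section 10.0, Arm 2):** difference 5, SD 8.9, correlation r = 0.3 with compound symmetry, alpha 0.05, and 27 (calculated) or 30 (targeted completers) per group. Two-sided testing is an assumption. Powers are two-sample noncentral t, with standard error SD × √(2/n).

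**Step 1. Reproduce the plan's figure.** For the mean of three measurements with no baseline subtracted:

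SD = 8.9 × √[(1 + 2 × 0.3)/3] = 8.9 × √(1.6/3) = 6.50.

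- At 27 per group, power is 79% by t and 81% by normal approximation. At 30 it is 83%.
- For 80% power, n per group is 27 (normal) or 28 (t) two-sided, and 21 or 22 one-sided. Two-sided testing is what fits 27.

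The arithmetic is therefore right for this contrast. That it is the contrast behind the plan's figure is an inference.

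**Step 2. Could the three measurements be Table 3's baseline, post and 1-month batteries?** No group difference is expected at baseline, so the averaged difference is (0 + 5 + 5)/3 = 3.33 with the same SD of 6.50. Power is 46% at 27 and 50% at 30 per group.

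**Step 3. The planned contrast, unadjusted, with 8.9 as a per-visit SD.** For change from baseline to the mean of k post visits:

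SD = 8.9 × √[1 + (1 + (k−1) × 0.3)/k − 2 × 0.3] = 8.9 × √[0.7 × (1 + 1/k)].

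**Step 4. The same contrast with 8.9 as the SD of a single change.** Under compound symmetry, changes that share a baseline correlate 0.5:

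SD = 8.9 × √[(1 + (k−1) × 0.5)/k].

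| Post visits averaged (k) | SD, step 3 | Power at 27 / 30 | SD, step 4 | Power at 27 / 30 |
|---|---|---|---|---|
| 1 | 10.53 | 40% / 44% | 8.90 | 53% / 57% |
| 2 | 9.12 | 51% / 55% | 7.71 | 65% / 70% |
| 3 | 8.60 | 55% / 60% | 7.27 | 70% / 75% |
| 4 | 8.33 | 58% / 63% | 7.04 | 73% / 77% |

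No entry reaches 80%. With a per-visit SD, the correlation needed for 80% at 30 per group is 0.71, 0.61, 0.56 or 0.53 for one to four post visits, against the plan's 0.3.

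**Step 5. Other readings.**

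- *Observations are change scores that themselves correlate 0.3:* at 27 / 30 per group, 71% / 76% for two, 79% / 83% for three and 84% / 87% for four.
- *One-sided 5% at 30 per group:* 57–74% (per-visit SD) or 69–86% (change SD).
- *Omnibus group x time test (per-visit SD, two to four post visits):* 42–45% at 30. This is not the pre/post contrast and is given for comparison only.

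**Step 6. With baseline adjustment at 30 per group (57 df).**

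SD = 8.9 × √[(1 + (k−1) × 0.3)/k − 0.3²].

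- k = 1: SD 8.49, power 61%.
- k = 2: SD 6.66, power 82%.
- If 8.9 is a change SD, the per-visit SD is 8.9/√1.4 = 7.52, and these become 76% and 92%.
- If the effect halves by the second visit, the average is (5 + 2.5)/2 = 3.75, and two-visit power is 57% (per-visit SD).

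A simulation of 20,000 runs at 30 per group with a per-visit SD agreed. Unadjusted power was 44%, 55% and 63% for k = 1, 2 and 4; adjusted power was 61% and 81% for k = 1 and 2.

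**The case against.** The strongest reply is that the plan names no contrast, so the mismatch is itself inferred. The SD is attached to a change and the model assesses change. If the three observations are post-treatment changes correlated 0.3, the claim is right: 79% at 27 and 83% at 30 per group. That stands as a possibility, but the text does not say it. Three post-treatment visits match neither neurocognitive schedule (four in the Arm 2 text, two in Table 3). The EEG schedule in section 9.0 does have three post-treatment visits, but it does not govern the neurocognitive outcome. Under the stated compound symmetry of raw scores, changes sharing a baseline would also correlate 0.5, not 0.3.

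A second reply is that a mixed model can adjust for baseline. With a per-visit SD, the average of two post visits then gives 82%, and averages of three or four give about 90% and 93%. This is correct and is the basis of the remedy. However, the plan specifies no adjustment, a single adjusted visit still gives only 61%, and the higher figures need an effect that persists.

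Third, sections 2.0 and 5.0 report that studies 1 and 2 were combined into Arm 4 with sponsor approval. If Arm 2 never runs, the loss of power never arises. This limits the consequence. Even so, sections 3.0, 5.0, 9.0 and 10.0 still carry Arm 2's recruitment target, procedures and power statement.

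**Conclusion.** The point holds. The stated 80% belongs to a comparison of averaged group levels, while the written test is an unadjusted group x pre/post change. At 30 per group, that test has 44–63% power with 8.9 as a per-visit SD and 57–77% with 8.9 as the SD of a single change. These figures assume two-sided 5%, a correlation of 0.3 between visits, a constant 5-point effect and no baseline adjustment.

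The conclusion would change if the plan stated that its three observations are change scores correlated 0.3, or if it specified baseline adjustment and averaged two or more post visits. One-sided testing would pass 80% only with a change SD and at least three post visits averaged (84–86%), and it does not fit the plan's 27. The point should be fixed while Arm 2 remains in the protocol; its practical weight is small if Arm 2 has been superseded.

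**What to change.** 1. Specify baseline adjustment in the Arm 2 mixed model, either with baseline as a covariate or with baseline means constrained equal.
2. Name the primary post-treatment visit or visits. State whether 8.9 is a per-visit or a change SD, state the sidedness, and restate power for that contrast. At 30 per group this is 61% for one visit (76% if a change SD), or 82% for the average of the immediate and 1-month visits (92% if a change SD). If the unadjusted change is kept, report 44–63% (57–77% if a change SD).
3. Reconcile section 2.0, the Arm 2 text in section 9.0 and Table 3 on follow-up visits.
4. State that the 5-point input is a before–after RBANS change in depressed patients, applied as an active–sham difference in healthy adults on a different battery.
5. If Arm 4 has replaced Arm 2, say so and remove the Arm 2 power claim.

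This is a change to the written analysis plan and adds no participants or visits: both the Arm 2 text and Table 3 already include the immediate and 1-month batteries. Averaging visits is optional. It changes the estimand and relies on persistence: if the effect halves by the second visit, power is 57%, against 61% for the first visit alone (per-visit SD). A single adjusted visit would need about 47 per group for 80%, so at the planned size the restated figure would be below 80%.

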Aim 2. Examine the efficacy and safety of accelerated rTMS to left dlPFC for enhancing cognitive performance and resilience. We hypothesize that relative to sham TMS, accelerated rTMS to left dorsolateral prefrontal cortex (dlPFC) will show neurocognitive performance (primary outcome) and resilience enhancements (secondary outcome) in a group of healthy adults that mimic the astronaut population. We additionally hypothesize that accelerated rTMS will be safe as indexed by 1) no clinically significant structural brain changes; 2) no decrements in neurocognitive or affective function; 3) no significant adverse events. We hypothesize that frontal midline theta (and intersite phase synchrony) will be enhanced during successful feedback learning as shown on post- relative to pre- treatment EEG and more so under stress. Under threat, we also expect to see reduced stress as indexed by physiological measures of defensive reactivity (autonomic and startles reflex responding). We additionally hypothesize that active stimulation will be related to lower levels of self-reported stress and neuropsychiatric symptoms and greater resilience.

Aim 3. Assess the biological efficacy of TMS in a microgravity environment. During parabolic flight, resting motor threshold (rMT) will be measured for 10 subjects and compared to rMT obtained before and after flight on the ground. Any change in rMT during flight compared with pre- and post-flight values will be interpreted as an indicator of an altered physiological response to TMS during microgravity and will guide extension of the optimal ground-based accelerated rTMS protocol for spaceflight.

[figure not shown]

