3.0 Study Endpoints

Study Arms 1 2 & 4 neurocognitive performance is the primary treatment outcome measure. Stress resilience and acceptability/tolerability are secondary treatment outcome measures. For Study Arm 3, biological efficacy of TMS in microgravity is the primary treatment outcome measure. Recruitment for Study Arm 1 will cease once 40 participants have completed all procedures and fulfilled randomization to all doses. Recruitment for Study Arm 2 will cease once 60 participants have completed all procedures and fulfilled randomization to all doses. Recruitment for Study Arm 3 will cease once 10 participants have completed all procedures. Recruitment for Study Arm 4 will cease once 50 participants have completed all procedures and fulfilled randomization to all doses.

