To assess the biological efficacy of TMS during microgravity, we will determine resting motor threshold (rMT) in 10 subjects before, during and following parabolic flight (sessions 1-3). To determine rMT, we will briefly apply single pulse TMS. We will use a standard clinical algorithm (adaptive parameter estimation by sequential testing) to determine rMT of the abductor pollicis brevis muscle in an automated fashion. The measurement takes 20 seconds to perform (20 stimuli using single pulse TMS)^{75,76}.

Pre-flight data collection: First, on the ground pre-flight, the optimal location for stimulus induction will be identified. This location will be marked on the scalp in order to facilitate quick and reproducible identification of this site during the in-flight and post-flight sessions. At this location the TMS coil will be fixed firmly in place and the rMT will be determined. The subjects will also undergo a 10 minute standard computerized cognitive battery (WinSCAT) used by NASA to assess cognitive function in astronauts during International Space Station flights⁶⁰.

In-flight data collection: The in-flight rMT measurement will be performed by placing the coil in the same location identified pre-flight. The coil will be secured in place using stabilization hardware developed with Zero-G similar to the fixation hardware in use in our lab. The flight profile includes 30 parabolas each with approximately 25 seconds of microgravity. This will allow up to 2-3 in-flight measurements per subject providing a margin for human error.

Post-flight data collection: The same procedure will also be utilized to obtain the post-flight measurement. The subjects will also undergo a computerized cognitive battery (WinSCAT) post-flight.

Any significant change (based on established values in normal controls⁵⁴) in rMT during flight compared with pre- and post-flight values will be interpreted as an indicator of an altered physiological response to TMS during microgravity.

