Arm 3. A power analysis was performed to determine the number of subjects needed to study physiological effects of simulated microgravity on motor threshold determination. With our study design, each subject will be his/her own control. For calculation of the study's power, we used data of Wassermann⁵⁴ who examined session-to session variability of motor threshold in 19 subjects on three separate occasions and computed the average coefficient of variation in motor threshold across sessions as 0.058 ± 0.036 . Based on this data, a total of 10 subjects will have a 99% chance (at a two sided 5% significance level) to detect a change in motor threshold due to an experimental intervention (parabolic flight) with an effect size of 1.61.

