Subjects will be exposed to TMS during parabolic flight for at most 40 seconds. However, as TMS has previously not been performed in a microgravity environment, all risks associated with TMS during parabolic flight cannot be known. Microgravity may result in unknown altered cerebral physiology which may alter the response to TMS and it is for this reason that study arm 3 is being performed.

Nevertheless, the investigators have taken several precautions to reduce the chance that a subject would be exposed to any serious risks from combined TMS and parabolic flight:

- First and foremost, only single pulse TMS will be performed. As discussed above, the risk of seizure induction with TMS is related to the intensity, duration, frequency and rest interval of stimulation. For study arm 3, only single pulse TMS will be performed such that TMS pulses will be spaced 1 second apart.
- The intensity of TMS will be very low. The intensity will be set to be at most just above the amount needed to cause a brief thumb twitch.
- The subjects will be exposed to a small number of TMS pulses (at most 40 TMS pulses total during parabolic flight)
- The duration of exposure to TMS during parabolic flight will be very brief. During parabolic flight, resting motor threshold will be determined. This will take at most only approximately 40 seconds total per subject.
- [name] will be present on the flight and in constant observation of the subjects. At any sign of an adverse event requiring medical attention, they will notify Zero-G flight personnel who will inform the pilot to end the parabolic flight maneuvers and return to the airport to get medical treatment for the subject. 911 will be called and emergency personnel will meet the team at the airport.

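### Arm 3's effect size of 1.61 appears to be the mean CV divided by its spread (0.058/0.036), not a paired change in motor threshold over its SD, so the cited data do not support 99% power

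*Combined protocol and SAP*

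**What the plan says.** Section 10.0 (Statistical Plan, Arm 3) makes each subject his or her own control. It takes its variability figures from one published study of 19 people measured in three sessions, and reports the "average coefficient of variation in motor threshold across sessions as 0.058 ± 0.036". From these figures it concludes that "a total of 10 subjects will have a 99% chance (at a two sided 5% significance level) to detect a change in motor threshold", for an effect size of 1.61. It gives no derivation of 1.61, no target change in rMT, no SD of a paired difference and no named test.

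The result carries weight. Section 3.0 states: "For Study Arm 3, biological efficacy of TMS in microgravity is the primary treatment outcome measure". Aim 3 in section 1.0 says that the rMT finding will guide how the ground protocol is extended to spaceflight.

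The decision rule is worded in two ways. Section 1.0 has "Any change in rMT during flight compared with pre- and post-flight values will be interpreted as an indicator of an altered physiological response". Section 9.0 has "Any significant change (based on established values in normal controls", followed by a literature citation. On replication, section 9.0 says of the flight profile: "This will allow up to 2-3 in-flight measurements per subject providing a margin for human error". It does not say whether repeat readings will be averaged.

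**The concern.** A paired effect size is the mean of the in-flight minus ground differences divided by the SD of those differences. The 0.058 describes how much rMT varies between sessions when nothing is done to the subject. The figure after the ± is not labelled; the natural reading is the SD of that variation across subjects. Their ratio contains no effect of flight and no SD of paired differences. It also behaves the wrong way: a sample in which everyone was measured equally badly would give a larger ratio, and so a higher apparent power.

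The 99% is the plan's only statement of what 10 subjects can detect, and it is not tied to any size of rMT change. A reader who takes it at face value may treat a non-significant result as good evidence that microgravity leaves the response to TMS unaltered. The plan gives no basis for saying which changes such a result would make unlikely.

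**Working it through.** **Inputs from the plan.** n = 10, two-sided 5%, effect size 1.61, CV 0.058 ± 0.036 (section 10.0). Each rMT reading uses 20 stimuli (section 9.0), and the ceiling is "at most 40 TMS pulses total during parabolic flight" (section 13.0). Two full readings use 2 × 20 = 40 pulses and a third would make 60, so the calculation stops at two in-flight readings.

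**1. Reproducing the 99%.** Paired t-test, df = 9, noncentrality = d × √10. With d = 1.61, power is 0.994. The stated 99% is therefore correct if the true standardised paired change is 1.61.

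**2. Where 1.61 comes from.** 0.058/0.036 = 1.611. No other figures given there yield 1.61. It was not solved backwards from the power, because exactly 99% at n = 10 needs d = 1.533.

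**3. What the cited CV can support.** Assumptions: the CV is the within-subject SD over the mean, it applies in flight, and errors are independent. With k in-flight and g ground readings averaged,

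SD of difference = CV × √(1/k + 1/g).

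Two summaries of the CV are used: the mean, 5.8%, and the root mean square, √(0.058² + 0.036²) = 6.83%, which treats 0.036 as an SD between subjects. At n = 10, 80% power needs d = 0.996 and 99% power needs d = 1.533, so the detectable change is d × SD.

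| CV | k | g | SD of difference | Change at 80% power | Change at 99% power | Expected 95% CI half-width | Power for a 5.8% change |
|---|---|---|---|---|---|---|---|
| 5.8% | 2 | 2 | 5.80% | 5.78% | 8.89% | 4.15% | 80% |
| 5.8% | 1 | 2 | 7.10% | 7.08% | 10.89% | 5.08% | 63% |
| 5.8% | 1 | 1 | 8.20% | 8.17% | 12.58% | 5.87% | 51% |
| 6.83% | 2 | 2 | 6.83% | 6.80% | 10.47% | 4.88% | 67% |
| 6.83% | 1 | 2 | 8.36% | 8.33% | 12.82% | 5.98% | 50% |
| 6.83% | 1 | 1 | 9.65% | 9.62% | 14.80% | 6.91% | 40% |

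The last column is an illustration only: 5.8% is the numerator of the apparent ratio, and the plan does not name it as a target. Simulation of the two extreme rows gave 0.804 and 0.399.

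**4. What d = 1.61 would mean in rMT.** From 1.61 × 5.80% = 9.3% to 1.61 × 9.65% = 15.5%. The plan neither states nor justifies a shift of that size.

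**5. Sensitivity (both inputs are assumptions).**
- If the two in-flight errors correlate at 0.5 (k = 2, g = 2), the SD is CV × √(0.75 + 0.5), that is 6.48% or 7.63%. The change detectable with 80% power is then 6.46% or 7.60%.
- If the same-day CV were 4%, that change would be 3.98% (k = 2, g = 2) to 5.63% (k = 1, g = 1).

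**6. Adequacy of n = 10.** Across the six rows, power for a 10% change runs from 0.830 to 0.998.

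**The case against.** The strongest defence is that the sentence is conditional. It says what power 10 subjects have at an effect size of 1.61, and that power is right. The division is nowhere shown, so the origin of 1.61 is an inference. Both points are true. But the plan presents the figure as following from the cited CV data, and even on the conditional reading it does not say what change in rMT 1.61 stands for.

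A second objection is that the substitute figures rest on assumptions too. The cited CV comes from separate sessions, whereas Arm 3 takes its flight-day readings on one day, at a marked scalp site with a fixed coil. In-flight noise could be lower or higher. With a 4% CV, the detectable change at 80% power falls below the range in the table. Averaging two in-flight readings is also not the plan's stated scheme, since section 9.0 describes the repeats as a safety margin. These points stand. They are reasons to give a range and to label it as conditional; they do not rescue the 1.61.

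Third, what a null result excludes depends on the observed confidence interval and not on planned power. That is correct, and it is why the interval belongs in the plan. Naming the test and aligning the decision rule go somewhat beyond the power sentence and are secondary to it.

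**Conclusion.** The concern holds. The match of 0.058/0.036 to 1.61 is an inference, though a strong one. Whatever its origin, the cited data give no change in rMT and no SD of paired differences, so they do not support a 99% chance of detecting a change due to flight.

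Taking the CV as within-subject SD over mean, with independent errors, 10 subjects have 80% power for a mean change of 5.8% to 9.6% of rMT and 99% power for 8.9% to 14.8%. The expected 95% interval extends about 4% to 7% either side of the estimate. These figures shift if same-day noise differs from the cited CV or if in-flight errors are correlated.

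The sample size is not shown to be inadequate. What needs correcting is the stated basis for it, and since this is the primary outcome of Arm 3, it should be corrected.

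**What to change.** In section 10.0, Arm 3:

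- Delete the 99% and the effect size of 1.61.
- State the assumed SD of the paired difference and its source, how many in-flight readings enter the analysis, and which ground readings they are compared with.
- Restate power as a detectable change in percent of rMT, labelled as conditional on those assumptions. With the cited across-session CV, this would be 80% power for about 6% to 10%, according to the averaging scheme. If a different same-day CV is assumed, recalculate.
- Name one group-level paired test of mean in-flight rMT against the mean of the pre- and post-flight values, reported with its 95% confidence interval.
- Align the two decision rules in sections 1.0 and 9.0 with that test, and say that a non-significant result excludes only changes outside the interval.

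The cost is wording in the protocol and SAP. No extra subjects, readings or flights are needed, though the stated power will look less favourable.
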